- Participants will be asked to fill out demographics information which will include their name (including name at birth), date of birth, city/town of birth, email and physical address, phone number, health history, and military history.
- Individuals without a medical record at the VA will be asked permission for study staff to request their medical record pertaining to sleep and traumatic brain injury.

Visit 2

- Visit 2 will occur ~2 weeks after visit 1. It can take place within the VAPORHCS Sleep Disorders Clinic (building 100-6C), in Research Service (building 101, rooms 432A, 430, 404, and 533), remotely via phone/video conferencing, or at the subject's home.
- *Questionnaires.* Subjects will complete baseline questionnaires. They take ~30 min to complete and include past medical history and self-reported measures on sleep, social habits, quality of life, mental health, pain, and other metrics related to subject's prior trauma exposure history. All questionnaires are validated and will be completed via pen and paper. Medical history and testing related to sleep will be accessed from the participants' VA medical records by study staff with VA credentials. Subjects may elect to complete these questionnaires at either this or subsequent visits as needed. Questionnaires may be mailed if completed remotely.
- *Equipment.* Subjects will be randomized to receive a lightbox (LightPad mini, Aurora Light Solutions) or sham-control modified negative ion generator. Devices will be modified by completely disconnecting the electrical wiring required for negative ion generation. This will be verified using a voltmeter. A small fan may be installed to emit a low humming noise as an indicator of activity. They will be instructed to use either device for 60 min every morning after waking up starting 2 weeks following this visit and continuing for 4 weeks. Light sensitive devices, called HOBOs, will be attached to the lightboxes which will track when the lightbox is turned on or off, as a secondary measure of light delivery.

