- *Pain testing.* Ischemic Pain Test. Ischemic pain testing may be used at VAPORHCS and at visits that are conducted remotely. This test will consist of a manual blood pressure cuff that is placed on the subject's non-dominant upper arm and inflated to 300 mmHg. Threshold will be determined by the amount of time that the subject perceives the constriction as mildly painful. Tolerance will be determined by the amount of time that the subject allows the constriction to continue. This will be done during a single trial. The upper limit of allowing the hand the constriction is 5 minutes.
- *Department of Defense Head Trauma Events Checklist (DoD HTEC).* Determination of TBI status occur through a semi-structured diagnostic interview following the DoD HTEC guidelines. This interview will take ~15 min to complete.
- *Reimbursement.* Subjects will be compensated with up to \$20

Visit 3

- Visit 3 will occur ~4 weeks after Visit 2 and will take place within the VAPORHCS Sleep Disorders Clinic (building 100-6C), in Research Service (building 101, rooms 432A, 430, 404, and 533), remotely via phone/video conferencing, or at the subject's home.
- *Measures.* The same series of questionnaires and pain testing conducted at Visit 1 will be repeated.
- *Equipment.* Subjects will return all equipment, including the actiwatch, lightbox and/or sham device.
- *Reimbursement.* Subjects will be compensated with up to \$60

Visit 4

- Visit 4 will occur ~4 weeks after Visit 3 and will take place within the VAPORHCS Sleep Disorders Clinic (building 100-6C), in Research Service (building 101, rooms 432A, 430, 404, and 533), remotely via phone/video conferencing, or at the subject's home.
- *Measures.* The same series of questionnaires and pain testing conducted at Visit 1 will be repeated.
- *Reimbursement.* Subjects will be compensated with up to \$20
- *End of study debrief.* Subjects will be debriefed about our experimental design, given the inclusion of a placebo-controlled condition. We will provide subjects with a written description that we will describe to them in person and address any questions they may have.

Mailed forms and equipment. In an effort to reduce subject's time at the Portland VA we may mail consent forms, questionnaires, equipment and pre-addressed, pre-paid return envelopes directly to their homes. Instructions will be provided via phone or video conferencing.

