The goals of our data management system are to maintain data accuracy and security, and to ensure efficient access for monitoring and analysis. All study personnel doing data collection will be carefully trained in their tasks (i.e., collection methods, security, auditing and tracking, prevention and detection of intrusion, back-up and recovery, quality control, monitoring and reporting.

Step-by-Step Guidance on Conducting the Study

Recruit subjects from methods described in “Subject Identification/Recruitment” section

1. Complete Visit 1.
 - a. Obtain written and verbal informed consent and HIPAA authorization from subjects
2. Schedule time to return to the VAPORHCS for Visit 2.
3. Complete Visit 2.
 - a. Provide subjects with lightbox or disabled negative ion generator
 - b. Collect subjects initial questionnaire data, complete pain testing, provide study diary
 - c. Compensate subjects with up to \$20
4. Schedule time to return to the VAPORHCS for Visit 3.
5. Complete Visit 3.
 - a. Collect subjects post-study questionnaire packet and complete pain assessment.
 - b. Collect subjects actiwatch, lightbox or negative ion generator, and study diary
 - c. Compensate subjects with up to \$60
6. Schedule time to return to the VAPORHCS for Visit 4.
 - a. Collect subjects follow-up questionnaire packet and complete pain assessment.
 - b. Compensate subjects with up to \$20
7. Thank subjects for their participation.

References & Literature Cited:

1. Centers for Disease and Control. Injury Prevention and Control: Traumatic Brain Injury and Concussion [Internet]. 2016. Available from: http://www.cdc.gov/traumaticbraininjury/get_the_facts.html
3. Okie S. Traumatic brain injury in the war zone. *N Engl J Med* 2005;352:2043–7.
4. Ouellet M-C, Savard J, Morin CM. Insomnia following Traumatic Brain Injury: A Review. *Neurorehabil Neural Repair* 2004;18(4):187–98.

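### Visit 2 is written in three conflicting orders, and the step-by-step guidance issues the allocated device before the baseline questionnaires and pain tests

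*Protocol*

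**What the plan says.** Three parts of the protocol describe Visit 2, the visit at which participants are randomised and baseline is taken.

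- **Step-by-Step Guidance on Conducting the Study, step 3.** Item 3a is "Provide subjects with lightbox or disabled negative ion generator". Item 3b is "Collect subjects initial questionnaire data, complete pain testing, provide study diary". Item 3c is payment.
- **Visit 2 narrative.** The Questionnaires item comes first ("Subjects will complete baseline questionnaires"). The Equipment item follows ("Subjects will be randomized to receive a lightbox (LightPad mini, Aurora Light Solutions) or sham-control modified negative ion generator"). Actigraphy, the diary, the three pain tests and the TBI interview come after it. The Questionnaires item also allows deferral: "Subjects may elect to complete these questionnaires at either this or subsequent visits as needed".
- **Study Overview and Timeline table.** The rows marked for Visit 2 run: actiwatch, pain assessment, lightbox or sham, questionnaires.

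Visits 3 and 4 each say "The same series of questionnaires and pain testing conducted at Visit 1 will be repeated", although the table shows no questionnaires or pain tests at Visit 1. No section says that baseline must be complete before allocation is revealed, and none describes a masked pain tester.

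**The concern.** A baseline value is protected by randomisation only if it is recorded before anyone who can influence it knows the allocation. Here the two arms receive objects that look different, and the baseline measures respond to expectation. The questionnaires are self-reported, the pain threshold is what the participant perceives as mildly painful, and tolerance depends on when the participant chooses to stop.

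If the device is handed over first, hope or disappointment about it can move the baseline differently in the two arms. So can the conduct of a tester who has seen which device was issued. The Specific Aims text says outcomes are assessed before and after the intervention, so the baseline is likely to enter the comparison, as a change score or as a covariate. An arm difference in baseline produced by knowledge of allocation would then pass into the estimated effect, and the analysis has no clean baseline with which to remove it.

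**Working it through.** The protocol gives no figure to reproduce. The check sets the three descriptions side by side.

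| Source | Listed order | Questionnaires relative to device | Pain tests relative to device |
|---|---|---|---|
| Step-by-Step Guidance, step 3 | device; questionnaires and pain tests; payment | after | after |
| Visit 2 narrative | questionnaires; randomisation and device; pain tests | before | after |
| Timeline table | pain assessment; device; questionnaires | after | before |

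1. Questionnaires follow the device in two of the three sources, and so do pain tests. No source puts both before it.
2. Step 3 can fairly be read as a sequence. The guidance for Visit 3 starts with "Collect subjects post-study questionnaire packet and complete pain assessment", then takes back the equipment, then pays, which is a natural order in time.
3. No rule elsewhere overrides the order. The deferral sentence in the Questionnaires item loosens it further. The paragraph on mailed forms and equipment lets both questionnaires and device go to the home without saying which is dealt with first.
4. The risk is not treatment exposure. The Equipment item has device use "starting 2 weeks following this visit and continuing for 4 weeks", so a baseline completed at Visit 2 precedes any use.

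How a disturbed baseline would act can be written down, though not sized. Let T be the true difference between arms at follow-up, d the arm difference in mean baseline caused by knowing the device, and b the slope of follow-up on baseline.

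- Post-treatment values alone: the estimate centres on T, so d does not enter.
- Change from baseline: T − d.
- Baseline-adjusted: T − b × d. With equal SDs, b is the correlation between baseline and follow-up.
- If the same expectation also shifts follow-up by e, the change score centres on T + e − d. A shift in the same direction partly cancels.

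Purely as an illustration, assume d = 0.1 to 0.3 SD, a correlation of 0.5 and e = 0. The displacement is then 0.1 to 0.3 SD for a change score, and 0.5 × 0.1 = 0.05 to 0.5 × 0.3 = 0.15 SD for an adjusted comparison. Neither assumed input has a basis in the protocol.

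**The case against.** The strongest reply is that these lists were not written as strict sequences. In the Visit 2 narrative the interview that determines TBI status comes last, after randomisation, so the items look grouped by topic. The guidance is loose too: step 3 omits the actiwatch that step 5 collects, and the Visit 4 activities sit under a scheduling step. Table rows need not be an order in time. Each kind of measure also precedes the device in one of the three sources.

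Much of this stands, and it limits the point. A reader might infer that every baseline outcome is taken after allocation in every participant. The documents do not support that: they conflict, and do not fix a device-first order throughout. But the reply does not supply the missing rule, and a section titled as step-by-step guidance is the one staff are most likely to follow.

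Other tempting inferences also fail:

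- *The participant knows the arm.* The participant knows which device was issued. The placebo condition is explained only at the Visit 4 debrief. Expectation can still differ between devices.
- *The tester knows the arm.* This is inferred from handover at the same visit and the absence of stated masking. The protocol does not say who tests or who hands over.
- *The reference to Visit 1 shows a late baseline.* It does not. Taken literally it would place baseline before allocation. It is a separate cross-reference error.
- *Randomisation no longer protects Aims 1 to 3.* This is too strong. A comparison of post-treatment values is untouched by a disturbed baseline, and the protocol does not fix a change-score or baseline-adjusted analysis.

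**Conclusion.** The point holds as a conflict between sections with a missing safeguard. Where the step-by-step order is followed, baseline questionnaires and pain tests come after the device is revealed. Where the narrative order is followed, the pain tests do. Expectation or assessor bias could then enter any comparison that uses the baseline.

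The size is unknown. A reader might divide the illustrative displacements by the effect sizes of 0.5 to 1.0 in the Power analysis and report a bias of 5% (0.05/1.0) to 60% (0.3/0.5) of the effect. That would only restate the assumed shift and correlation and should not be quoted as an estimate.

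The conclusion rests on two conditions: that staff follow a written order that puts the device first, and that the analysis uses the baseline. Severity: should be fixed. The defect is avoidable and cannot be undone once data are collected, but the protocol does not show that it will affect every participant or every analysis.

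**What to change.** 1. In the Step-by-Step Guidance, reverse 3a and 3b.
2. In the Visit 2 narrative, move the Equipment item after the pain tests.
3. In the timeline table, the Visit 2 narrative and the guidance, state the same rule, for example: *Baseline questionnaires and pain tests are completed before the allocation is revealed and the device is issued or, for remote participants, before it is mailed or opened.* Bring the sentence that lets questionnaires be completed at later visits into line with it.
4. Separately, correct the references to Visit 1 under Visits 3 and 4 to the visit at which baseline is taken.

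For visits in person the cost is a change of order within Visit 2, with no added procedure. For remote participants the device would be shipped later, or kept unopened until baseline is done, which is a modest change in logistics. The reordering does not reach actigraphy: the watch is issued at the same visit as the device, so any baseline actigraphy still follows allocation.

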Appendix – Supporting Documents List

Contact info sheet filled out by subjects at consent
Demographics form
Modified HTEC
Flyer

Info sheet given to subjects
Questionnaire packet
Phone scripts

DocuSign Materials: Phone Script E-consenting,
Letter DocuSign Memo for PO,
IAM Stand Alone eSig service training

Email Script for DocuSign,
SOP DocuSign for Research,
